Increased knowledge on actual attrition factors and patterns in adolescent populations from mHealth interventions are direly needed. Obtaining a better understanding of how motivational support motivates adolescents to use mHealth applications and why they maintain or lose interest in using them to improve their health is of vital importance. Motivational support in mHealth interventions, defined as strategies to enhance motivation and counter attrition to overcome behavior change barriers, often include goal-setting, feedback, social support and rewards (36-37). Systematic reviews examining possible drivers behind usage point to group and task customization, localization, functional user support, gamification of health tasks and immediate visual but simplified feedback on user action while while gender-related motivational support features could be contributing factors [36-38]. Timing of tailored motivational support, through just-in-time adaptive interventions (JITAI), should be considered as well when implementing adolescent mHealth interventions since time-based individualization could counter high attritions rates [35, 39]. Given the magnitude of reported health problems among adolescents and lack of cost-effective health behaviour interventions specifically developed for adolescent populations, the need for better understanding of attrition reasons in adolescent mHealth interventions is massive. The purpose of this study was firstly to seek richer understanding of continuous attrition rates from a mHealth intervention in an adolescent population and what effects motivational support has on attrition rates. Secondly, the aim was to examine effectiveness of the intervention with the aim to increase daily mental, nutritional and physical health behaviour.

Methods

Participants

Participants are adolescents, age 13 to 16 years old, attending one of three public schools for children and adolescents in the greater capital area of Iceland. All children attending the oldest 3 classes, called 8th to 10th classes, in three participating public elementary schools in

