
Figure 1. Overview of app functions & categories

[figure not shown]

Procedure

The study is a randomized controlled study. Cluster randomization is used to distinguish three participating schools into control, treatment-as-usual (TAU) and intervention groups. Measures will be obtained at baseline and 42 days later. Participants in both the TAU group and the intervention group receive an approximately 10 minutes long introduction regarding the study specifications and the application. The control group receives no further contact, access to the application or information until study-end questionnaire measures. Participants in the intervention group are randomly assigned to teams consisting of 8 individuals that collectively and individually compete in point collection through completion of in-app health tasks. Participation in the TAU group and intervention group is defined as downloading the Sidekick app and completing at least 3 health exercises within it. Time of exercise is defined as the timestamp on completion of exercise within any of the three types of exercise categories (physical activity, nutrition and mental health) of the app. Exercise frequency refers to how often a given exercise was completed by a participant. Time of attrition was defined as the time stamp of last completing health exercise within the Sidekick throughout intervention period. The procedural difference between TAU group and intervention group evolves around motivational support. The intervention group receives weekly motivational support in form of individual and group feedback on usage, participation in friendly health task competitions and weekly altruistic rewards for usage. Participants in TAU group use the

application individually throughout trial period without any motivational support. A flow chart of participation is displayed in figure 2.

Figure 2. Participant flow chart

Statistical analysis

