Descriptive characteristics of participants along with attrition reason are reported. Pearson's correlation coefficient, independent samples *t*-tests, repeated measures ANOVAs with adjusted alpha levels, and χ^2 tests will be used to measure mean differences from baseline to trial's end within and between research groups on primary and secondary outcome measures. Kaplan-Meier survival analysis plots and logrank tests are deployed to assess time of attrition and possible significant differences between and within research groups [50, 51]. Trial beginning is defined as time of first in-app health exercise completion and the trial period was six weeks, or 42 days, from that moment. Attrition, or the event, is defined as the time of participants' last completed health exercise in SidekickHealth. Participants' cases will be evaluated as censored when the application was still being used 42 days after study start. Cox proportional hazard regression models with interacting covariables using research groups as clusters was used to examine attrition prediction based on usage of in-app health exercises between time, type and frequency of exercises as well as sociodemographic variables (age,

gender) [52]. Significance will be defined at $p < .05$. Data was analysed using IBM SPSS Statistics, Release Version 29 (SPSS, Inc., 2009, Chicago, IL, USA, <http://www.spss.com>).

References

1. Smith, A. (2015, April 1). *U.S. Smartphone Use in 2015*. Pew Research Center. <https://www.pewresearch.org/internet/2015/04/01/us-smartphone-use-in-2015/>
2. Silver, L. (2019, February 5). *Smartphone Ownership Is Growing Rapidly Around the World, but Not Always Equally*. Pew Research Center <https://www.pewresearch.org/global/2019/02/05/smartphone-ownership-is-growing-rapidly-around-the-world-but-not-always-equally/>
3. Anderson, M. & Jiang, J. (2018, May 31). *Teens, Social Media and Technology 2018*. Pew Research Center. <https://www.pewresearch.org/internet/2018/05/31/teens-social-media-technology-2018/>
4. Jones, E. A. K., Mitra, A. K. & Bhuiyan, A. R. (2021). Impact of COVID-19 on Mental Health in Adolescents: A Systematic Review. *The International Journal of Environmental Research and Public*, 18(5). <https://doi.org/10.3390/ijerph18052470>
5. Körmendi, A. (2016). Smartphone usage among adolescents. *Psychiatria Hungarica: A Magyar Pszichiátriai Társaság Tudományos Folyóirata*, 30(3), 297-302.

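### Change is tested for significance within as well as between groups, and the plan never says that effectiveness rests on the between-group difference in change

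*Combined protocol and SAP*

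**What the plan says.** The second aim, at the end of the introduction, concerns effectiveness: "Secondly, the aim was to examine effectiveness of the intervention with the aim to increase daily mental, nutritional and physical health behaviour". It names no deciding comparison.

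Under Procedure, "Cluster randomization is used to distinguish three participating schools into control, treatment-as-usual (TAU) and intervention groups", so there is one school per arm. "Measures will be obtained at baseline and 42 days later" gives two time points. The control school has no app and is contacted again only for the study-end questionnaires.

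Under Statistical analysis, one sentence lists Pearson's correlation, "independent samples *t*-tests", "repeated measures ANOVAs with adjusted alpha levels" and chi-square tests. All are to measure mean differences from baseline to trial end "within and between research groups on primary and secondary outcome measures". The section later adds "Significance will be defined at" p < .05. It does not give the size of the alpha adjustment or the family it covers. No section gives the group-by-time term priority or limits within-group change to description.

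**The concern.** A within-group p-value asks whether pupils in one school changed over 42 days. The effectiveness aim asks whether they changed more than they would have without the app or its motivational support. The two questions differ whenever scores move for reasons common to all schools, for example because pupils answer the same questionnaire a second time or because the season has changed. The comparison schools are there to remove such movement, and a within-group test does not use them.

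Because the plan tests both kinds of change and does not say which one decides, the effectiveness aim could be declared met from a within-group result when all three schools changed by the same amount. The same risk attaches to reading a significant change in the intervention school beside a non-significant one in the control school as if it were a difference between them.

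**Working it through.** **Inputs.** The document gives no sample size target, SD, effect size or power, so there is no design figure to reproduce. It offers two rough cues on size:

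- 661 eligible pupils (313 + 348) in three schools, so 661 / 3 ≈ 220 per school if the schools are equal in size.
- A reward cost of 50 to 100 US dollars at about 0.50 each, so 50 / 0.50 = 100 to 100 / 0.50 = 200 participants. The text does not say which arms these cover.

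**Assumptions.** 50, 100 or 200 pupils analysed per arm; no app effect; the same drift δ in every arm, with δ = 0.1, 0.2 or 0.3 SD of the change score; independent pupils; two-sided 0.05 (the plan does not state sidedness).

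**Step 1: within-arm test.** A correct paired t-test of change has n − 1 degrees of freedom and noncentrality δ√n. For n = 100 and δ = 0.2 the noncentrality is 0.2 × 10 = 2.0. The probability P of a significant result is then 0.508.

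**Step 2: intervention significant, control not.** With equal arms and the same drift this is P(1 − P). For n = 100 and δ = 0.2: 0.508 × 0.492 = 0.250.

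| n per arm | δ (SD of change) | Intervention arm's own change significant | Intervention significant, control not |
|---|---|---|---|
| 50 | 0.1 | 10.7% | 9.5% |
| 50 | 0.2 | 28.4% | 20.3% |
| 50 | 0.3 | 54.8% | 24.8% |
| 100 | 0.1 | 16.8% | 14.0% |
| 100 | 0.2 | 50.8% | 25.0% |
| 100 | 0.3 | 84.4% | 13.2% |
| 200 | 0.1 | 29.1% | 20.6% |
| 200 | 0.2 | 80.4% | 15.8% |
| 200 | 0.3 | 98.8% | 1.2% |

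The third column rises steadily with n and δ. The fourth peaks at 25% when P = 0.5 and falls once every arm is likely to be significant.

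**Step 3: between-arm test of change.** The expected difference in mean change is δ − δ = 0, so shared drift cancels. In 20,000 simulated trials for each of the nine settings, the two-sample t-test on change scores rejected in 4.8% to 5.4%.

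**Step 4: adjusted alpha.** Taking 0.05 / 3 ≈ 0.0167 as an example, n = 100 and δ = 0.2 still give a significant within-arm change in 33.6% of trials. The adjustment limits false rejections of true null hypotheses. Here the hypothesis of no change over time is false, so rejecting it is correct, but it says nothing about the app.

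**The case against.** The strongest reply is that the plan never says a within-group change will be called an effect of the app. Speaking of change within and between groups is also ordinary language for a mixed repeated measures ANOVA, which yields the group-by-time test. That stands. A reader might infer that the sponsor intends to claim effectiveness from within-group p-values, and the document does not support that. What remains is that the same ANOVA also yields a time effect, and nothing says which term decides.

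A reader might also infer that every test is run at an unadjusted 0.05. The ANOVAs carry an adjustment, and they are the only paired procedure listed, so a within-group test might well use it. Step 4 shows why that does not help.

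The sizes rest on assumed values, and the contrast of a significant intervention arm with a non-significant control arm is not always a large risk: at 200 per arm and a drift of 0.3 SD it is about 1%. Regression to the mean and school events are poor examples of the mechanism. Pupils are not selected on extreme scores, since all pupils in the three oldest classes are eligible apart from the stated exclusions. School events usually affect one school only.

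Finally, the between-group contrast has limits of its own. In-app outcomes do not exist in the control school, and arm and school are fully confounded. Both points stand. They limit what the recommended contrast can show, but they lend no support to the within-group test.

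**Conclusion.** The concern holds as a gap in the plan: change is tested within groups as well as between them, and no deciding contrast is named for the effectiveness aim. With 100 analysed per arm, a shared drift of 0.1 to 0.3 SD of the change score makes the intervention arm's own change significant in about 17% to 84% of trials with no app effect; with 200 per arm, about 29% to 99%. The direction does not depend on the assumed sample size or drift, but the percentages do.

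A reader might conclude that naming the between-group contrast makes the comparison of schools valid. That goes too far. Its rejection rate near 5% assumes independent pupils and no drift peculiar to one school, and one school per arm cannot secure either.

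**What to change.** In the Statistical analysis section, replace the wording that puts within-group and between-group tests side by side with:

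> Conclusions on effectiveness rest only on the between-group difference in change (group-by-time contrast) with 95% CI: among all three groups for outcomes measured in all three, and intervention versus TAU for in-app outcomes, which the control school cannot provide. Within-group changes are descriptive, shown as means with 95% CI, and are not evidence of effect.

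Add a sentence stating that, with one school per arm, this contrast removes drift shared by the schools but not drift specific to one school.

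The change needs no new data. Its cost is that the sponsor gives up quoting a significant within-group change as an effect.

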SidekickHealth was initially developed through multiple focus group studies amongst both Icelandic elementary school students and adolescents in the obesity clinic at the Landspítali University Hospital in Iceland to incorporate the target groups' needs and opinions. Based on results from focus-group studies and design advisors, the app took the form of a social health game (see Figure 1). Functionality of the app evolves around motivational support to help the user set goals and complete health tasks (gamification of tasks), in three main categories: food and drink (e.g. vegetable and water intake, consumption of fruits, avoiding sugary soda or energy drinks), physical activity (e.g. body-weight exercises, logged minutes of sports activity, gps-based biking, walking or running), and mental health exercises (e.g. reducing stress, exercising gratitude and improving sleep habits). By completing health tasks that are labelled missions and participating in friendly competitions with peers, users earn points (called "kicks") and badges providing altruistic rewards (e.g. litres of water for children in need or polio vaccinations that are sent in their name to children in need through UNICEF). A visual representation of the user's performance is provided in different categories. Keeping the app fun, entertaining, and easy-to-use is of integral importance and was a strong focus point throughout all developmental phases. The smartphone application operates on Android and iOS platforms. The app's function focuses on education and simple health behaviour changes through the benefits of increased physical activity and mental health exercises as well as a healthy diet, portion sizes, and appetite awareness training (AAT). AAT is a behaviour modification tool that has for instance been used in obesity treatment and encourages overweight/obese children and youth to consume food and drink in response to internal appetite cues. It has shown promise for the treatment of overweight and obese children and teenagers and has been visually developed as an individual mission in the app's nutrition category [48, 49]. Participants in the intervention realm will be randomly assigned to groups consisting of 8 individuals which collectively and individually competed in point collection through completion of in-app health tasks. In the beginning of each of the trial's 6 weeks, the intervention group receives in-app messages where a new weekly competition (both individual and on group level) with altruistic rewards is introduced. In weeks 2 to 6, altruistic rewards for past week's efforts will also be handed out. Winners of competitions receive confirmation that UNICEF had sent Polio vaccinations to children in need. Further, through completion of in-app health exercises participants collect litres of water that will be sent in their name to children in need through UNICEF. The total cost for the altruistic rewards for all in-app rewards throughout the treatment period was roughly estimated to be between 50 to 100 US dollars or roughly 50 US cents per participant.

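### The attrition Cox model names the research arms as its clusters, and no planned attrition analysis accounts for the teams of 8 in the intervention arm

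*Combined protocol and SAP*

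**What the plan says.** **Design.** The Procedure section states: "Cluster randomization is used to distinguish three participating schools into control, treatment-as-usual (TAU) and intervention groups". Each arm is therefore one school. Controls have no access to the app, so only the TAU and intervention arms can supply app-attrition data.

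**Delivery.** In the same section: "Participants in the intervention group are randomly assigned to teams consisting of 8 individuals that collectively and individually compete in point collection". It adds: "The intervention group receives weekly motivational support in form of individual and group feedback on usage". The mHealth application section says that each week "a new weekly competition (both individual and on group level) with altruistic rewards is introduced". TAU pupils, by contrast, use the "application individually throughout trial period without any motivational support".

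**Analysis.** The Statistical analysis section plans Kaplan-Meier plots and logrank tests for "possible significant differences between and within research groups", and then "Cox proportional hazard regression models with interacting covariables using research groups as clusters was used to examine attrition prediction". The predictors it lists for the Cox model are the time, type and frequency of exercises, plus age and gender. Teams are not mentioned anywhere in that section.

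**The concern.** Teams exist in one arm only, so the design is partially nested. Shared competition and group feedback give team-mates a reason to keep using the app, or to stop, together. The natural independent unit is then the team in the intervention arm and the pupil in the TAU arm. The plan uses neither. It names the arms as clusters for the Cox model and leaves the logrank test unadjusted.

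The study's first stated purpose is to understand attrition and how motivational support affects it. The Cox and logrank analyses are the only methods assigned to time of attrition and its prediction, so their error rates decide whether that aim can be answered.

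**Working it through.** The plan gives no sample size, event count, hazard ratio or intraclass correlation (ICC), so there is no figure of its own to reproduce.

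**Inputs from the documents.** Team size is 8, two arms have app data, follow-up is 42 days and alpha is 0.05 (two-sided assumed). The mHealth application section puts reward cost at 50 to 100 USD, at about 0.50 USD per participant. That implies 50/0.50 = 100 to 100/0.50 = 200 pupils, or about 13 to 25 teams, if the line refers to the rewarded arm.

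**Assumptions.** Arms are of equal size. Team ICC and team log-hazard SD are not given, so a range is shown.

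**Reading A: *clusters* means a cluster-robust variance.** At the fitted values the score contributions of the two arms sum to zero. The middle of the sandwich then has rank one, however many pupils there are. The size was checked by simulating a Cox model with no true effects:
- 1,500 runs per scenario, with 13 or 25 teams of 8 against an equal-sized TAU arm;
- covariates for arm, gender and one continuous variable correlated within teams;
- censoring at 42 days and 76-81% events.

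Type I error at nominal 5%, 13 teams / 25 teams:

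| Team log-hazard SD | Clustered on arm: arm term | Clustered on arm: gender | Model-based: arm term | Model-based: gender | Model-based: team-correlated covariate | Clustered on team: arm term |
|---|---|---|---|---|---|---|
| 0 | 87.7 / 92.1% | 40.1 / 41.6% | 5.1 / 5.4% | 4.3 / 4.5% | 4.3 / 5.1% | 6.3 / 5.7% |
| 0.3 | 88.7 / 91.7% | 40.3 / 40.1% | 7.5 / 8.8% | 5.4 / 5.3% | 5.1 / 5.3% | 6.3 / 6.8% |
| 0.5 | 88.9 / 92.8% | 38.5 / 40.8% | 10.5 / 10.7% | 6.3 / 4.8% | 7.5 / 7.1% | 6.2 / 4.7% |
| 0.8 | 92.5 / 93.8% | 39.2 / 39.6% | 18.3 / 17.3% | 4.3 / 3.9% | 8.1 / 9.6% | 7.3 / 5.9% |

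With arms as clusters, the standard error was 3-6% of the true sampling SD for the arm term and 45-50% for the individual covariates. The first row shows that this happens with no team correlation at all.

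**Reading B: *clusters* means strata or a grouping label.** The standard errors are then model-based and ignore teams, as the logrank test does. In closed form, for a mean with equal arms and teams in one arm only:
- design effect in the intervention arm: DE = 1 + (8 - 1) x ICC;
- variance ratio for the arm contrast: r = (DE + 1)/2;
- true type I error: 2 x [1 - Phi(1.96/sqrt(r))].

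| ICC | DE | r | SE factor sqrt(r) | Type I error |
|---|---|---|---|---|
| 0.01 | 1.07 | 1.035 | 1.017 | 5.4% |
| 0.05 | 1.35 | 1.175 | 1.084 | 7.1% |
| 0.10 | 1.70 | 1.350 | 1.162 | 9.2% |
| 0.20 | 2.40 | 1.700 | 1.304 | 13.3% |

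The model-based columns of the simulation show the same pattern. The arm term is affected, a covariate that is correlated within teams is affected less, and gender stays at about 4-6%.

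**After the change.** Clustering on team, with TAU pupils as singletons, gave 4.7-7.3% over all scenarios and covariates. Having few teams explains the excess over 5%.

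**The case against.** **The plan names no robust variance.** This stands. A reader might infer that the Cox standard errors are certainly unusable as written. The documents do not support that, because the phrase could also mean strata or a grouping factor, and Reading A's figures apply only if a sandwich variance is meant.

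**Arm is not a listed Cox predictor.** This also stands. Between-arm attrition is assigned to the logrank test. The 88-94% therefore applies only if an arm term is fitted, and 38-42% is the figure for individual covariates. For the same reason, losing the arm effect under stratification is not in itself a clear defect of that model.

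**Teams do not cause the large figures.** Correct. Two clusters are too few whatever happens inside teams. It would be wrong to read 88-94% as the cost of ignoring teams; that cost is the Reading B range.

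**The team effect may be small.** Teams are formed at random, so correlation can arise only from what happens after assignment. The documents imply such interaction but give no ICC. At 0.01 the error is 5.4%, which is harmless. At a team SD of 0.3, clustering on team lowers arm-term error only from 7.5-8.8% to 6.3-6.8%.

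***Research groups* might mean the teams.** The mHealth application section does call the sets of 8 groups. However, the Statistical analysis section uses the full phrase for its between-group and within-group comparisons, and the Procedure section calls the sets of 8 teams. If teams were meant, the plan would still have to say how TAU pupils, who have none, are handled.

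**Clustering on team does not rescue the arm comparison.** This stands. A school ICC of only 0.01 (assumed), with 104 pupils per arm, gives a design effect of 1 + 103 x 0.01 = 2.03 and type I error of about 17%, before any team correlation.

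**Conclusion.** The point holds in a limited form. The plan delivers support partly through teams in one arm, names the arms as Cox clusters, and tests attrition between arms without regard to teams. No reading of the Cox sentence, together with the unadjusted logrank test, gives valid between-arm inference on attrition unless team-mates are independent.

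The size depends on the reading. With a cluster-robust variance on two arms, type I error is 38-42% for individual covariates, and 88-94% for an arm term if one is fitted. With strata or a label, it is 5.4% to 13.3% for the arm contrast over team ICCs of 0.01 to 0.20, with age and gender little affected. These figures rest on assumed ICCs, equal arms and, for the simulation, 13 to 25 teams. If the team ICC were zero, only the cluster-robust reading would remain wrong on this account.

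A reader might infer that the trial's attrition comparison becomes sound once teams are modelled. The documents do not support that, since arm and school are the same thing in this design.

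**What to change.** In the Statistical analysis section, replace the clause that makes research groups the clusters with wording such as: *arm will be entered as a covariate; the variance will be robust and clustered on the team of 8 (or a shared team frailty will be fitted), with each TAU pupil as a cluster of one and a small-sample correction for the number of teams.* Keep the Kaplan-Meier plots, but take the between-arm p-value from this team-clustered test and not from the plain logrank test.

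Add one sentence stating that this corrects for team correlation only and that, with one school per arm, the arm effect remains confounded with school.

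The cost is a change of wording and keeping the team identifier, which team assignment already creates. It should be confirmed that the software named in the section can fit the model. Intervals will be somewhat wider if teams are correlated. Extending the same adjustment to the questionnaire comparisons is optional; it would mean replacing the planned t-tests and ANOVAs and is not needed for this point.

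### The Cox model predicts attrition from an exercise count with no time window; counted over the whole follow-up, frequency looks protective by construction and can distort the age, gender or group terms

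*Combined protocol and SAP*

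**What the plan says.** The Statistical analysis section specifies "Cox proportional hazard regression models with interacting covariables using research groups as clusters" in order to "examine attrition prediction based on usage of in-app health exercises between time, type and frequency of exercises", and lists age and gender alongside these usage variables.

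The two definitions that matter are in Methods, Procedure:

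- Predictor: "Exercise frequency refers to how often a given exercise was completed by a participant". No period, denominator, landmark or time-updated coding is given there or elsewhere.
- Event: "Time of attrition was defined as the time stamp of last completing health exercise within the Sidekick throughout intervention period". The Statistical analysis section repeats this, starts the clock at the first completed exercise, and censors pupils still using the app at day 42.

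The end of the Introduction makes attrition the first aim, including "what effects motivational support has on attrition rates". Kaplan-Meier plots and logrank tests are planned for comparing groups. The Cox model is the only planned analysis of usage as a predictor of attrition.

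**The concern.** Predictor and event time come from the same log over the same period, and a pupil stops adding to the count at the event itself. If frequency is one fixed total, its value is known only once the pupil has quit or reached day 42, so the model uses the future to predict the past. A longer stay produces a larger count, and the model reports the larger count as the reason for the longer stay.

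A significant protective hazard ratio would then be reported whether use has no bearing on quitting, retains pupils, or wears them out. The analysis could not tell these apart, and later app design could be guided by an artefact. A covariate in the same model that is related to use, such as gender, or group if entered, is distorted as well. A real benefit of motivational support would be hidden to the extent that support raises use.

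**Working it through.** **No planned figure to reproduce.** The document gives no sample size, event count, retention or hazard ratio for this model. The check is the algebra of the definitions, then simulation with assumed inputs.

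**Direction.** Let r be a pupil's exercises per day, T the days of activity and N the total count, so N is about r × T. Suppose r has no effect on T. At each event time t, the pupil who leaves has expected count r × t, while everyone remaining has T > t and so a larger expected count. Leavers therefore have the lower counts at every event time, and the fitted HR falls below 1. A pupil active for 40 days has 40/5 = 8 times the opportunity to log exercises of one active for 5.

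**Other covariates.** At equal N, T is about N/r. If one gender has 1.5 times the rate, its members at the same count stayed about 1/1.5 = 0.67 times as long. The model reads that as a higher hazard even if gender has no effect on quitting.

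**Assumed inputs.**

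- App users: n = 100, 200 and 440. The mHealth application section puts rewards at "between 50 to 100 US dollars or roughly 50 US cents per participant": 50/0.50 = 100 and 100/0.50 = 200. This covers rewarded pupils only, since the treatment-as-usual group uses the app "application individually throughout trial period without any motivational support". The upper value is 661 × 2/3 = 441, used as 440, and assumes equal schools and full uptake; neither is stated.
- Quit times: exponential, means 14, 35 and 60 days, censored at 42. exp(-42/14) = 5% and exp(-42/60) = 50% remain; the entry rule of at least 3 exercises removes early leavers, so retention among those analysed is 5-55%.
- Use: Poisson with gamma-varying rates (shape 2), means 0.5, 1 and 3 a day. First exercise at time 0; event at the last exercise.
- 3 × 3 × 3 = 27 scenarios, 1,000 runs each (500 for the group runs with a use ratio of 1.0 or 1.25 and for count divided by time), alpha 0.05.

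**Results with the whole-follow-up count.**

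| Truth | Result |
|---|---|
| Use unrelated to quitting; count + age + gender | Significantly protective in 99-100%; HR 0.64-0.93 per 5 exercises |
| Same, with group and a count-by-gender interaction added | Count terms significant in 97-100% |
| Same, count of one exercise type | Significantly protective in 96-100% |
| Heavier users quit sooner (HR 1.5 per doubling of rate) | Still significantly protective in 76-100% with age and gender, 67-100% alone |
| Gender raises use 1.5-fold, no effect on quitting | Gender HR 1.32-1.44; falsely significant in 21-33% at n=100, 61-80% at n=440; 3-7% without the count |
| Group HR 0.70, equal use | Group HR 0.71-0.76 (0.69-0.74 without the count) |
| Group HR 0.70, support raises use 1.25-fold | Group HR 0.85-0.90 |
| Group HR 0.70, support raises use 1.5-fold | Group HR 0.97-1.04 |

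**Sensitivity to the 1.5-fold figure.** At 1 exercise a day, with the same quit means and values of n (400 runs each, count + gender), gender was falsely significant in 8-17% at a 1.1-fold difference, 13-27% at 1.2-fold and 24-79% at 1.5-fold; with equal use, 6-11%.

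**Separate check with other inputs** (median stay 7, 14 or 28 days; 1-2 exercises a day; 300 runs in each of seven scenarios). A count with no true effect was significant in 100% of runs in all seven, HR 0.65-0.85 per 10 exercises. With a true group HR of 0.60 and 1.5-fold use in that group, the group HR became 0.88 and power fell from 83% to 10%.

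**Dividing the count by days of use.** This does not cure it. The entry rule alone gives a pupil who leaves after 1 day a rate of at least 3/1 = 3 a day, while a 42-day user can have 3/42 = 0.07. High rates then go with early exit: null rejection 23-100%, with HR above 1.

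**Day-7 landmark count.** Null rejection was 6-8% at n=100, 5-10% at n=200 and 5-12% at n=440, and 4-7% for gender. A smaller run (150 repeats) reached 16% in one setting with 0.5 exercises a day and n=440. When heavier users truly quit sooner, the direction was right in 98-100%, significant in 57-100%, and never significant in the wrong direction.

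**The case against.** The strongest objection is that the coding is inferred. How often can mean a rate, and the recorded time stamps would allow time-updated coding. That is fair as to the sign of the bias, which is established only for a whole-follow-up count. It does not rescue the plan: the per-day rate is biased the other way, so an unstated choice decides the direction of the result.

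Second, the plan speaks of models in the plural and uses research groups as clusters. Age and gender could be fitted apart from usage, and if group is only a stratum or a variance term there is no group coefficient to distort. This stands, so the distortion of these terms is conditional. The wording about interacting covariables does favour joint entry.

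Third, the logrank test still answers the group question, and attrition predictors are not among the primary outcomes listed under Measurements. Both are true. The harm is to the usage-prediction part of the first aim, which has no other planned analysis.

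Fourth, the 1.5-fold difference in use has no source in the document. The size depends on it, as the sensitivity figures show; the direction does not.

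Fifth, a landmark leaves some residual bias and cannot explain week-1 quitting. That is a real cost. Finally, parts of the section are in the past tense. If the data have already been analysed, a window set now would be post hoc.

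**Conclusion.** The concern holds and should be fixed before the Cox results are relied on. As written, the usage predictor has no exposure window. On the natural reading it grows with its own outcome time, and a protective result is then near certain (99-100% of runs) with no true effect and likely (76-100%) even when the truth is the reverse. The direction follows from the document's definitions; the sizes rest on the assumed numbers of users, retention and use rates, and are not forecasts for this trial. Distortion of age or gender requires that they share the model with the count and differ in use; distortion of group requires in addition that group enters as a covariate. Kaplan-Meier, logrank and Cox models without usage counts are not affected.

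**What to change.** In the Statistical analysis section, state that usage predictors are measured before the risk period, and give the window. One suitable rule: exercise frequency is the number of exercises completed in days 0-7 after the first exercise; the model includes participants whose attrition time is after day 7, with time counted from day 7. Day 7 is illustrative; fix the day before analysis, or label the choice as post hoc if data have been examined. Apply the same window to counts by type and to time of exercise.

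Estimate age, gender and group associations in a separate Cox model without post-start usage. Keep all participants in that model and in the Kaplan-Meier and logrank analyses.

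A time-updated 7-day count can serve as a sensitivity analysis only. Its window must exclude the exercise that defines the event: null rejection was 11-100% with that exercise included and 6-30% with it excluded (200 runs in each of 18 scenarios, n=100 and 200).

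Cost: two or three sentences and a recoding of logs already time-stamped. Under the assumed inputs, day 7 removes 7-37% of participants and 16-39% of events from the usage model only, leaving about 38-63 events at n=100, 75-126 at n=200 and 165-278 at n=440. Day 3 would lose 5-17% of events but leave null rejection as high as 23% at n=440; day 14 would lose 38-65% of events, with null rejection up to 11%. Some bias remains with sparse use, because a sparse user must stay longer to log an exercise after the landmark.
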